### 5.6.1 Permitted Concomitant Medications

Following screening and enrollment, ancillary medications (ibuprofen, acetaminophen, methocarbamol, hydroxyzine, and loperamide) may be administered to subjects to help alleviate signs and symptoms of opioid withdrawal as deemed necessary by the Investigator or medically qualified sub-investigator. Details on acceptable administration of these medications and preparations are provided below:

- Ibuprofen (400 mg orally) may be given every 4 to 6 hours as needed for pain up to a maximum of 2400 mg per day. Subjects for whom ibuprofen is contraindicated or not tolerated may be given acetaminophen (325 to 1000 mg every 4 to 6 hours) as needed up to a maximum of 3000 mg per day. Caution should be exercised when using acetaminophen concomitantly with other medications that have potential hepatotoxic effects. Methocarbamol may also be given as needed for relief of muscle pain in clinically appropriate doses based on physician assessment.
- Hydroxyzine (50 to 100 mg orally) may be given every 6 hours as needed for anxiety, nausea, or vomiting. Additionally, hydroxyzine (50 to 100 mg orally) may be given at bedtime as needed for sleep. The hydroxyzine daily dose should not exceed a maximum of 600 mg per day.
- Loperamide (2 to 4 mg orally) may be given as needed for diarrhea up to a maximum of 16 mg per day.

### 5.6.2 Prohibited Concomitant Medications

Concomitant therapies subject to the restrictions indicated under Prohibited Concomitant Medications may be used only following approval by the Sponsor unless an immediate medical need necessitates their use. These are listed below:

- Use of buprenorphine.
- Ongoing prescription that are clinically relevant P450 3A4 inducers or inhibitors, such as azole antifungals (e.g., ketoconazole) and macrolide antibiotics (e.g., erythromycin).

- Herbal supplements that have the potential to cause prolongation of the QTc interval.
- Over-the-counter medications that have the potential to cause prolongation of the QTc interval. This does not apply to over-the-counter medications listed under Concomitant Therapies above that are prescribed by the Investigator, or over-the-counter medications that may be used by the Investigator for an immediate medical need that necessitates their use. The medical monitor should be consulted for any questions.
- Medications, in the addition to those listed above, which may be expected to significantly interfere with the metabolism or excretion of buprenorphine that may be associated with a significant drug interaction with buprenorphine, or may pose a significant risk to subjects' participation in the study.

Other concomitant medications, OTC preparations, or therapies that are not allowed during study participation are listed in [Appendix 9](#).

## 5.7 Restrictions

### 5.7.1 Prior Therapy

All prior medications including OTC, dietary supplements, and herbal preparations taken by the subject within the 30 days prior to screening will be recorded.

### 5.7.2 Subject Activity Restrictions

Subjects should be advised to avoid strenuous exercise.

## 5.8 Protocol Compliance

This study involves the SC injection of multiple doses of RBP-6000 containing 100 or 300 mg of buprenorphine (see the Schedule of Events [SOE], [Appendix 2](#)). The Investigator may terminate a subject based on the subject's inability or willingness to comply with the protocol requirements.

IMP will be administered by designated and qualified study personnel at the site. The time and duration, the dose delivered, and any dosing observations will be recorded in source documentation. The Investigator or designated individual will maintain a log of all study drugs dispensed and returned (if applicable). Drug supplies will be inventoried and accounted throughout the study.

## 5.9 Packaging and Labeling

RBP-6000 will be packaged and labeled in a manner consistent with the study design and applicable regulations. The study medication will be provided to the investigator(s) by the Sponsor or contractor.

The SUBOXONE sublingual film will be supplied as bulk films in the following buprenorphine dosage strengths: 2mg /0.5 mg; 4 mg/1 mg; 8 mg/2 mg; and 12 mg/3 mg. Containers will be

labeled with a single panel disclosing the product name, lot number, contents, Sponsor name and address, route of administration, and appropriate precautionary statements.

The study drug, RBP-6000, will be identified as an investigational compound.

The following components will be used in the preparation of RBP-6000:

- One sealed foil pouch containing a syringe prefilled with RBP-6000 and an oxygen absorber pack.
- One sterile 19-gauge, 1 inch hypodermic safety needle.

## **5.10 Storage and Accountability**

RBP-6000 should be stored under refrigerated conditions between 2-8°C (36-46°F). Temperature excursions between 8 and 25°C (46 and 77°F) are permitted for a maximum duration of 48 hours; Temperature excursions between 2 and -20°C (-4 and 36°F) are permitted for a maximum duration of 7 days. Temperature excursions outside of these ranges or timeframes should be reported to the Sponsor immediately and approval for use should be obtained.

SUBOXONE sublingual films should be stored at 25°C (77°F) with excursions permitted between 15-30°C (59-86°F). Temperature excursions outside of these ranges should be reported to the Sponsor immediately and approval for use should be obtained.

The PI or designee is responsible for ensuring that all study drug received at the site is inventoried and accounted for throughout the study. Drug accountability is the responsibility of the PI or designee, with verification by the CRA. Study drug must be handled strictly in accordance with the protocol, handling guidelines and the label, and must be stored in a locked, limited access area under appropriate environmental conditions. The PI must ensure that proper conditions exist for storage of study treatments. The dispensing of study drug to the subject must be documented on the drug dispensing form.

Unused study drug must be available for verification by the Sponsor's site monitor during on-site monitoring visits. The return to the Sponsor of unused study drug will be documented on the Study Drug Return Form.

The Investigator agrees not to supply RBP-6000 to any person except study personnel for SC injection of subjects in this study.

## **5.11 Investigational Product Retention at Study Site**

The PI or medically-qualified designee agrees to conduct a study drug supply inventory for RBP-6000, to record results of this inventory, and to return all unused study drug to the Sponsor at times specified by Indivior. Indivior will arrange for the appropriate and timely destruction of all returned, unused RBP-6000. All used needles and syringes from RBP-6000 will be disposed of into an appropriate secure biohazard container per the standard operating procedures (SOPs) at the study site.

All used IMP packaging (e.g. carton, foil pouch) will be retained at the study site until reconciliation is performed by the CRA. After reconciliation is completed, the used IMP packaging may be disposed of per the SOPs at the study site.

## 6 STUDY PROCEDURES

The SOE for this study is provided in [Appendix 1](#), [Appendix 2](#), [Appendix 3](#), [Appendix 4](#), and [Appendix 5](#).

For roll-over subjects, study procedures completed at EOS/Day 169 for study RB-US-13-0001 will serve as screening assessments for the open-label study.

### 6.1 Informed Consent

#### 6.1.1 General Information

Prior to entering the study, the Investigator or designated individual must explain to each subject the nature of the study, its purpose, procedures, expected duration, alternative therapies available, and the benefits and risks involved in study participation. Subjects must be given the Institutional Review Board (IRB)-approved ICF version to review and the opportunity to ask questions. Subjects must be informed of their right to withdraw from the study at any time without prejudice. The potential subjects should be able to answer simple questions about the study after the ICF has been reviewed and explained. After this explanation and before any study-specific procedures have been performed, the subject must voluntarily sign and date the ICF to indicate the desire to participate in the study. Prior to participation in the study, the subject must receive a copy of the signed and dated ICF.

Roll-over subjects will complete all Day 169/EOS procedures for study RB-US-13-0001 prior to signing the ICF for this study.

### 6.2 Medical History

For *de novo* subjects, a detailed medical history will be obtained by the PI or medically qualified designee during the screening visit (Visit 1). This will include information regarding the subject's full history of medical and psychiatric conditions, diagnoses, procedures, treatments, concomitant medications, demographic information, and use of tobacco, drugs of abuse, alcohol, and caffeine, and any other noteworthy medical information, including suicidality measured using the eC-SSRS. Any updates to medical history information that the PI or medically qualified designee becomes aware of will be captured throughout the study. All prior medications, OTC health, and dietary supplements taken by the subject within 30 days will be recorded. In addition, hospitalizations in the past 3 months and the reason for admission (medical/surgical/psychiatric/other) will be recorded.

For roll-over subjects, medical history will not be obtained again.

### 6.3 Physical Examination

A complete physical examination (PE) will be performed by the Investigator or medically qualified designee. The physical examination will consist of an examination of the following: general appearance, skin, head, eyes, ears, nose, throat, neck (including thyroid), lymph nodes, chest and lungs, heart, abdomen, extremities, body weight, and a brief neurological assessment.

The examination will not include a pelvic, breast, or rectal examination. If any clinically significant abnormal findings started before the date that informed consent was given, these findings should be recorded on the Medical History case report form (eCRF).

If any clinically significant change from screening (Visit 1 for *de novo* subjects; Study RB-US-13-0001 EOS visit (Day 169) for roll-over subjects) is noted, it will be reported as an AE and followed up to resolution or until reaching a stable end point.

Weight (kg) will be assessed (in ordinary indoor clothing with shoes off) and will be recorded at screening as well as periodically throughout the study. Height (cm) will be recorded at screening only. BMI will be calculated at screening as well as periodically throughout the study. BMI is defined as the subject's weight in kg divided by the square of the subject's height in meters (kg/m^2). The amount of abdominal fat will be measured using the waist-to-hip ratio and will be recorded at screening as well as periodically throughout the study.

Procedures performed at Day 169/EOS in the RB-US-13-0001 study will not be repeated at the screening visit for roll-over subjects.

Assessments are performed at the time points detailed in the SOEs ([Appendix 1](#), [Appendix 2](#), [Appendix 3](#), [Appendix 4](#), and [Appendix 5](#)).

## 6.4 Vital Signs

Evaluation of vital signs will be performed after the subject has been supine for  $\geq 3$  minutes and will include a measurement of systolic and diastolic BP, pulse rate, pulse oximetry, respiratory rate, and oral temperature.

If clinically significant findings, as determined by the Investigator or medically qualified sub-investigator, occur in any vital sign measurement, that measurement will be captured as an AE and repeated at medically appropriate intervals until the value returns to an acceptable range, a specific diagnosis is established, or the condition is otherwise explained.

Assessments will be recorded in the source documents and eCRF and will be performed at the time points detailed in the SOE ([Appendix 1](#), [Appendix 2](#), [Appendix 3](#), [Appendix 4](#), and [Appendix 5](#)).

## 6.5 Electrocardiograms

### 6.5.1 12-Lead Electrocardiograms

Resting 12-lead ECGs will be recorded with the subject in supine position following a 10-minute rest period. For roll-over subjects, ECGs will be recorded prior to the PK blood sampling. ([Appendix 6](#)).

Resting 12-lead ECGs will be recorded as indicated in the SOEs ([Appendix 1](#), [Appendix 2](#), [Appendix 3](#), [Appendix 4](#), and [Appendix 5](#)). ECGs recorded at screening will be recorded in triplicate, at approximately 2 - 5 minute intervals.

ECG intervals including HR, QT, QTcF, QTcB, RR, PR, QRS and T wave changes will be recorded. ECGs will be reviewed by the Investigator during the visits for any immediate abnormalities. ECGs will also be reviewed by a central facility.

The findings of the ECGs as determined by the central facility will be assessed by the Investigator and marked as normal, abnormal-not clinically significant, or abnormal-clinically significant. All clinically significant abnormalities will be captured as AEs. In the event that a clinically significant AE related to an ECG assessment occurs during the study, the Investigator should contact the Indivior Medical Monitor.

## **6.6 Clinical Laboratory Tests**

### **6.6.1 Laboratory Parameters**

All clinical laboratory assessments will be performed by a clinical laboratory accredited by the College of American Pathologists or with a certificate of compliance (or certificate of waiver for CLIA-waived tests) issued by the Center for Medicare & Medicaid Services or Clinical Laboratory Improvement Amendments. The laboratory assessments will include routine and screening laboratory tests.

See the SOEs in [Appendix 1](#), [Appendix 2](#), [Appendix 3](#), [Appendix 4](#), and [Appendix 5](#) for the timing of the specific required laboratory tests which are listed in [Table 2](#).

Any abnormal hematology, chemistry, or urinalysis test result deemed clinically significant by the Investigator will be repeated, including test results obtained on the final study day. For any test abnormality deemed clinically significant, an AE will be recorded (unless the result was considered erroneous) and repeat analysis will be performed until resolution or until the Investigator determines that resolution of the laboratory abnormality is not expected.

Subjects will be in a seated or supine position during blood collection. Clinical laboratory panels are listed in [Table 2](#).

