The suicidal ideation intensity rating is the sum of the five intensity item scores to create a total score (range 0 to 25). The five intensity items include frequency, duration, controllability, deterrents, and reason for ideation. Each item is scored from 0 to 5 with 5 representing the most severe intensity.

Suicidal Behavior Scoring

The suicidal ideation score ranges from 0 to 5 and depends on the answers to the suicidal behavior portion of the eC-SSRS. The score is the maximum suicidal ideation category (in the following order: 1 = preparatory acts or behavior, 2 = aborted attempt, 3 = interrupted attempt, 4 = actual attempt, and 5 if the subject has an AE with a preferred term of completed suicide. If all answers to these questions are "No" and the subject does not have an AE with a preferred term of completed suicide then the suicidal behavior score is 0.

Treatment Duration (weeks)

Treatment duration will be defined as $(\text{treatment stop date} - \text{treatment start date} + 1)/7$ where treatment stop date is defined as date of last RBP-6000 injection + 28 days.

Sponsor: Indivior Inc.
 Protocol no: RB-US-13-0003

Percentage of Urine Drug Screen and Self-Report Results

Subjects' self-reported illicit drug use from the TLFB and results from the UDS will be combined into a single endpoint in the following manner:

- If both the TLFB and the UDS have a negative result at a particular visit, then the visit will be considered to have a negative result at that visit.
- If either the TLFB or UDS, or both, have a non-negative result at a particular visit, then the visit will be considered to have a non-negative result at that visit.
- To be conservative, missing UDS or TLFB data will be imputed as non-negative.

Urine Drug Screen Result for Opioids	Self-Report of Illicit Opioid Use Result	Overall Result
Nonnegative	Nonnegative	Nonnegative
Nonnegative	Negative	Nonnegative
Negative	Nonnegative	Nonnegative
Negative	Negative	Negative

Treatment Success

A subject is defined as a treatment success if $\geq 80\%$ urine samples negative combined with self-reports negative.

Visit Window for Remapping of Early Termination visit

Duration will be derived in days as (ET visit date – treatment start date) + 1.

Sponsor: Indivior Inc.
 Protocol no: RB-US-13-0003

Visit window for safety and efficacy assessments.

Study Visit	Lower Window for Analysis Day (ADY)	Upper Window for ADY
Week 1 Day 1	1	1
Week 1 Day 2	2	5
Week 2 Day 8	6	12
Week 3 Day 15	13	19

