Week 4 Day 22	20	26
Week 5 Day 29	27	38
Week 7 Day 43	39	54
Week 9 Day 57	55	68
Week 11 Day 71	69	82
Week 13 Day 85	83	94
Week 15 Day 99	95	110
Week 17 Day 113	111	122
Week 19 Day 127	123	138
Week 21 Day 141	139	166
Week 25 Day 169	167	194
Week 29 Day 197	195	222
Week 33 Day 225	223	250
Week 37 Day 253	251	278
Week 41 Day 281	279	306
Week 45 Day 309	307	335

If an ET visit/assessment happens any time between Day 1 and prior to End of Study visit, the following approach (Table) should be adopted to remap those ET visit to applicable study visit week based on the ADY variable value, defined as date of assessment – date of first dose + 1, of the ET date variable.

If Lower Window <= ADY (of ET date) <= Upper window, then set appropriate AVISIT value based on the above CRF study visits.

After re-mapping the ET visits to any of study visit weeks, if there are multiple records falling within the same week window, latest one with non-missing result will be flagged in analysis datasets and considered for analysis of by visit summary tables and figures.

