9.0 Statistical Methods

All statistical analyses will be performed using SAS® Version 9.4 or higher.

Categorical variables will be summarized using counts and percentages. Percentages will be rounded to one decimal place; except 100% will be displayed without any decimal places and percentages will not be displayed for zero counts. When assessments are not applicable (ie Post injection 6 visits for roll-over subjects), an N/A will displayed instead of a zero,

Sponsor: Indivior Inc.
Protocol no: RB-US-13-0003

Continuous variables will be summarized using the number of observations (n), mean, standard deviation (SD), median, minimum, and maximum. The minimum, maximum, and 95% CI values (in some instances) will be displayed to the same level of precision as the raw data, the median and mean to one additional decimal place and the SD to two additional decimal places. The maximum number of decimal places will be 4. All summaries will be presented by subject type (de novo or roll-over) unless otherwise stated.

Unless otherwise stated, summaries will be presented by subject type (de novo or roll-over and total). Missing values will be presented by blank spaces. For partially missing dates, the information present will be printed; e.g., "--JAN2000".

For dichotomous outcome measures such as urine drug screen results (negative; non-negative) and self-reports for illicit opioid use (negative; non-negative), any missing observation will be set equal to "non-negative." Missing results for substances other than opioids will not be imputed. For all continuous endpoints (e.g., COWS, SOWS, and VAS), the missing data will not be imputed.

Only scheduled assessments per protocol Amendment 4 will be presented in tables and figures except for worst case post-baseline and at any time types of analyses (all post-baseline including unscheduled assessments data will be considered for this derivation) but all data will be presented in the listings.

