9.6.2 Laboratory Data

Laboratory data will be reported using International System (SI) units as collected by the central laboratory. Unless otherwise specified, all continuous laboratory data will be summarized using descriptive statistics (n, mean, SD, median, min, and max) for each scheduled study assessment as well as change from baseline and percentage change from baseline [if applicable] by parameter class (hematology, chemistry, and urinalysis). The following parameters will have graphs of the mean values by visit through the end of study: hematocrit, alkaline phosphatase (ALP), alanine aminotransferase (ALT), amylase, lipase, trypsinogen, aspartate aminotransferase (AST), creatinine clearance, creatinine kinase, gamma-glutamyl transferase, and bilirubin (from serum chemistry results). All laboratory assessments include a baseline summary as defined in [Section 5](#) unless otherwise indicated. Hematology, chemistry, and urinalysis data will be summarized by displaying shifts from baseline value (low/normal/high) to last assessment on treatment and worst result on treatment (for only subjects with normal as baseline) considering both scheduled and unscheduled assessments. All laboratory assessments will be listed by panel with the corresponding normal ranges for each parameter. Screening laboratory will be provided in a separate listing.

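### SAP 9.6.2 and 9.0 disagree on whether unscheduled laboratory repeats enter the shift-to-last table; if they do, any bias in end-of-treatment status is toward normal

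*Protocol*

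**What the plan says.** **When a test is repeated (Protocol 6.6.1).** A hematology, chemistry or urinalysis abnormality "deemed clinically significant by the Investigator will be repeated, including test results obtained on the final study day". The stopping rule has two arms: "repeat analysis will be performed until resolution or until the Investigator determines that resolution of the laboratory abnormality is not expected". The section orders no repeat for a normal result, or for an abnormal one judged not clinically significant. Each clinically significant abnormality is also recorded as an AE unless the result is considered erroneous.

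**What the shift tables use (SAP 9.6.2).** Low/normal/high shifts run from baseline "to last assessment on treatment and worst result on treatment (for only subjects with normal as baseline) considering both scheduled and unscheduled assessments".

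**The general rule on unscheduled data (SAP 9.0).** "Only scheduled assessments per protocol Amendment 4 will be presented in tables and figures except for worst case post-baseline and at any time" types of analysis. All data go into the listings.

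**End of treatment (SAP 5.0).** For treatment duration, "treatment stop date is defined as date of last RBP-6000 injection + 28 days". SAP 9.4 uses the same span for exposure. Neither section applies it to laboratory data, and SAP 9.6.2 gives no definition of its own.

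**The concern.** Changes in laboratory results are a primary variable (SAP 4.1), and the shift-to-last table is the one that shows, across all three panels, who ends treatment outside the normal range. Under SAP 9.6.2 the record that represents a subject can depend on the result itself. A clinically significant abnormality at the final scheduled test leads to further tests, the last of which may be normal. A normal final result leads to nothing. The replacement therefore works in one direction.

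The two SAP sections also cannot both be followed. One programmer applying 9.6.2 and another applying 9.0 could produce different counts from the same data.

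The worst-result shift does not fully cover the gap, because it is limited to subjects normal at baseline. For subjects abnormal at baseline, shift-to-last is the only shift table. Such subjects can enrol: Protocol 4.3 excludes de novo subjects only from ALT or AST of 3 x ULN upward, and the roll-over criteria in 4.2 and 4.3 list no laboratory limits.

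**Working it through.** The documents state no figure for these tables and no formal sample-size calculation (Protocol 9.2), so there is nothing to reproduce. Three checks were made.

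**1. Who can be affected under each reading of *on treatment*.** The nominal last injections are Day 141 for roll-over ("Week 21 Day 141" in the SAP visit windows) and Day 309 for de novo. Nominal EOS is Day 169 and Day 337, window -2/+4 days (Protocol Appendices 3 and 5).

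- Treatment stop under the 28-day rule: 141 + 28 = Day 169; 309 + 28 = Day 337. Both equal nominal EOS.
- Days left on treatment after the visit = 28 - (days from last injection to visit), not below 0.

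| Visit | Days after last injection | Days left, 28-day rule |
|---|---|---|
| EOS 2 days early | 26 | 2 |
| EOS nominal | 28 | 0 |
| EOS 4 days late | 32 | 0 |
| ET | 7 | 21 |
| ET | 14 | 14 |
| ET | 21 | 7 |

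With a 30-day limit, as in the TEAE definition, the three EOS rows become 4, 2 and 0. So for a completer, a repeat of the EOS result almost never counts, while for an early terminator it can. Repeats earlier in the study are overtaken by the next scheduled test, 2 to 4 weeks later. Subjects brought to EOS mid-interval by early study closure (Protocol 3.3) would be in the same position as early terminators. With no upper limit on treatment, any repeat after EOS/ET counts.

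Read strictly, the 28-day cut-off would also exclude an EOS sample drawn late in its window. The last injection visit, or a repeat of it, would then be the final on-treatment record.

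**2. How large the effect could be.** Reported abnormal share = p x (1 - c x w x r), where p is the share abnormal at the last scheduled test, c the share of those judged clinically significant, w the share of those whose closing repeat counts as on treatment, and r the share of those repeats that are normal. All four are assumptions. The second stopping arm enters through r: repeats that stop without resolution stay abnormal. With p = 10% and r = 80%:

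| c | w | Calculation | Reported |
|---|---|---|---|
| any | 0% | 10% x 1 | 10.0% |
| 30% | 10% | 10% x (1 - 0.024) | 9.8% |
| 10% | 100% | 10% x (1 - 0.08) | 9.2% |
| 30% | 100% | 10% x (1 - 0.24) | 7.6% |
| 100% | 100% | 10% x (1 - 0.80) | 2.0% |

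Using the last scheduled value gives 10.0% throughout. The relative understatement runs from 0% to 80%, driven by w (the meaning of *on treatment*) and c.

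**3. Whether a normal repeat needs a true recovery.** Assume a bivariate normal model with no true change and the upper limit at z = 1.96, and compute P(repeat ≤ 1.96 | first > k). For k = 1.96 the probability is 0.41, 0.56, 0.67 and 0.82 at within-subject correlation 0.9, 0.8, 0.7 and 0.5. For k = 3 it is 0.02, 0.15, 0.32 and 0.64. Some normal repeats would therefore reflect regression to the mean alone. The correlations are assumed.

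**The case against.** The strongest reply is that no settled biased analysis has been shown. If SAP 9.0 governs, or if the closing phrase of the 9.6.2 sentence qualifies only the worst result, unscheduled repeats stay out of shift-to-last and there is no bias. That stands: the documents show a conflict, and the bias follows only on one reading, although the specific section would usually prevail.

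A reader might infer that clinically significant abnormalities vanish from the report. The documents do not support that. Each is an AE unless erroneous, all results are listed, and the worst-result shift includes it for subjects normal at baseline. By-visit summaries cover the end-of-study visit, and SAP 9.6.2.2 gives liver and pancreatic threshold counts at each time point and at any point. What these leave uncovered is narrower: low/high status at the end of treatment for the remaining tests, and shifts for subjects abnormal at baseline.

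It can also be said that a later normal value may be genuine recovery or the correction of a spurious result, and that regression to the mean makes a single unrepeated high value overstate persistent abnormality. This is fair, so the bias is relative to status at the scheduled end-of-treatment test. But a value drawn later, only because the earlier one was abnormal, is not comparable with other subjects' scheduled values.

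Finally, most low/high flags may never be judged clinically significant and so never be repeated. That limits the size but does not change the direction.

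**Conclusion.** The point holds as an inconsistency between SAP 9.0 and 9.6.2, with a missing definition of *on treatment*. If 9.6.2 is followed, any resulting bias in end-of-treatment status is toward normal, because only clinically significant abnormal results are re-tested. Under a cut-off of last injection + 28 days it concerns mainly early terminators; with no cut-off it can concern anyone re-tested after EOS/ET.

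A reader might go further and conclude that end-of-treatment abnormalities will be understated across the study, or by a large fraction. The documents do not establish either. They leave open which SAP rule applies, they allow re-testing to end with the value still abnormal, and they give none of the four quantities needed to size the effect. The 0% to 80% range rests wholly on assumed inputs and shows only what the answer depends on. The change is worth making because it is cheap and applies the SAP's own general rule.

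**What to change.** In SAP 9.6.2:

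- Define *on treatment* for laboratory data, stating explicitly that the EOS/ET sample is included.
- Base the shift-to-last table on the last scheduled post-baseline result up to and including EOS/ET. A repeat ordered because a result was abnormal does not replace that result. Results marked erroneous may be dropped.
- Use unscheduled results only in the worst-result and any-time tables, consistent with SAP 9.0.

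The cost is about one sentence and one record-selection flag, with no new data and no change to re-testing. Shift-to-last counts may become slightly less favourable, and a true recovery seen only on a later repeat will appear in the listings rather than in this table.
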